### **1.3.2. Known potential benefits**

This study enrolls metastatic or recurrent patients who have failed standard therapy. Its benefit for patients who participate in this study remains unclear. However, based on prior study of ramucirumab in gastric cancer patients who have failed first-line chemotherapy, ramucirumab monotherapy improves overall survival up to two months[13]. When ramucirumab was tested at different doses in metastatic patients with different cancer types, 60% had stable disease with median duration of 12.7 months[10, 14]. Stable disease  $\geq 4$  months occurred in 20% of patients without warning toxicities. Based on similar mode of action, we expect the activity of HLX06 likely to be similar to that of ramucirumab.

## **2. OBJECTIVES**

### **2.1. Primary Objective**

To identify safety and the maximum tolerated dose (MTD) of HLX06 in patients with advanced or metastatic tumors refractory to standard therapy.

### **2.2. Secondary Objectives**

- The pharmacokinetics of HLX06 at different doses in patients.
- The pharmacodynamics of HLX06 at different doses in patients.
- The immunogenicity of HLX06 in human beings.
- The anti-tumor effects of HLX06 in patients.
- The potential prognostic and predictive biomarkers of HLX06 for advanced solid tumors.

### **3. OVERVIEW OF STUDY DESIGN AND ENDPOINTS**

#### **3.1. Description of the Study Design**

This study is a prospective, open-label, dose-escalation study of HLX06 in patients with metastatic or recurrent solid tumors who have failed standard therapy.

This study integrates the modified accelerated titration design 2A (ATD) and Bayesian optimal interval design (BOIN) to determine the MTD of HLX06[1, 2]. The safety and PK profiles, and immunogenicity as well as the preliminary efficacy will also be examined.

Eligible patients who fulfill the eligibility criteria will receive weekly infusion of HLX06 at the assigned dose level until disease progression or to the maximum of one year, withdrawal from study or death, whichever comes first.

Each cycle of treatment is comprised of 4 doses of investigational product administered weekly.

This study plans to enroll a maximum of **30** patients. *Patients who withdraw from the study for reasons not related to treatment-emergent toxicities during the first cycle will be replaced.*

##### **3.1.1. Accelerated titration design and cohort size**

In the ATD 2A design, the study starts with acceleration phase. In this phase, each cohort consists of one NEW patient for each dose level. After first cycle of treatment, the patient will be evaluated for the toxicities in last cycle. If this patient does not have DLTs, the next patient is allowed to receive the treatment at the next higher dose level.

In the acceleration phase, the newly enrolled patients start at the highest dose level, in which no moderate toxicities are observed in prior patients.

When the first instance of first-cycle DLT or the second instance of first-cycle grade $\geq 2$  toxicities of any types occurs, acceleration phase ends and the cohorts for the current dose level expand to three NEW patients and the study switches the BOIN design phase.

In the acceleration phase, intra-patient dose escalation is NOT allowed.

##### **3.1.2. Bayesian optimal interval design and rules of dose escalation and de-escalation**

After the acceleration phase, the study uses BOIN design to determine rule of dose escalation and de-escalation. First, the target toxicity rate in this study is set at **30%**, which is the most

common toxicity rate for conventional 3+3 design, indicating that for an oncologic agent, the toxicity rate higher than 30% is NOT desirable[15].

Different from the rule-based 3+3 design, the decision to escalate or de-escalate in BOPIN design is based on the posterior probability of DLTs from updated information. The probability of DLTs is determined by the number of DLTs and the cumulative number of patients treated at the current dose. The safety boundary to escalate the dose is set at 70% of target toxicity rate (i.e. 21%); and the toxicity boundary is, at 130% of target toxicity rate (i.e. 39%), respectively. If the probability of DLTs at the current dose level falls below 21%, the dose in the next cohort escalates to the next higher level. By contrast, when the probability of DLT at the current dose level arises above 39% (130% of target rate), the dose in the next cohort de-escalates to the next lower level. The dose level for the next cohort remains the same if the probability of toxicity is within the safety and toxicity boundary. The enrollment continues until the maximum of 30 patients are reached.

The detailed rule of dose escalation and de-escalation is tabulated in Table 1.

There are also two pre-set EARLY STOPPING RULES in this study.

- Stop the trial if the lowest dose (dose level 1) is eliminated due to overt toxicities.
- Stop the trial and estimate the MTD if the number of new patients treated at the current dose level reaches 15

The detailed statistical methods for dose escalation and de-escalation and estimation of MTD are described in Section 11. This study uses R software and BOPIN package for setting up the specifications. The detailed R codes for this study are described in the Appendix (Section 15.5).

Patients who experience DLTs may be allowed to continue the treatment at the next lower dose level after the toxicities revert to grade $\leq 1$  in 28 days after last infusion, if the Investigator judges that the patient still meet the inclusion criteria and might benefit from continuous treatment.

*For patients who experience DLTs, re-escalation to the dose level causing DLT is not permitted. Up to two dose-level reductions per patient are allowed in this study.*

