### **Dose escalation/de-escalation rule and Bayesian optimal interval design (BOIN)**

After the end of acceleration phase, the decision to escalate or de-escalate in subsequent cohorts is based on the numbers of patients experiencing DLTs and the total number of patients treated at the current dose level (Table 1). The decision to escalate or de-escalate is based by pre-defined safety and toxicity boundary. If the probability of the DLT rate falls below the safety boundary, the dose for the next cohort escalates. By contrast, if the probability of DLTs arises above the toxicity boundary, the dose de-escalates in the next cohort. Otherwise, the dose level stays the same in the next cohort. The enrollment continues until the maximum of 30 patients is reached. The safety boundary in this study is set at 21% (70% of target rate); and the toxicity boundary, at 39%, (130% of target rate), respectively. The detailed rules are described on page 19 . A hypothetical scheme of ATD and BOIN design in the 30 patients is shown in Figure 1.[2]

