**Table 1. Dose escalation table**

No. of patients treated at current dose level	3	6	9	12	15
Escalate if # of DLT	0	1	2	3	3
Remain at the same dose if # of DLT	1	2	3	4	4,5
De-escalate if # of DLT	2	3	4	5	6
Eliminate if # of DLT	3	4	6	7	8

The rules to escalate or de-escalate are as follows:

- (a) “Eliminate” means that we eliminate the current and higher doses from the trial to prevent treating any future patients at these doses because they are overly toxic.
- (b) When we eliminate a dose, we automatically de-escalate the dose to the next lower level. When the lowest dose is eliminated, we stop the trial for safety. In this case, no dose should be selected as the MTD.
- (c) If none of the actions (i.e., escalation, de-escalation or elimination) is triggered, we treat the new patients at the current dose.
- (d) If the current dose is the lowest dose and the rule indicates dose de-escalation, we will treat the new patients at the lowest dose unless the number of DLTs reaches the elimination boundary, at which point we will terminate the trial for safety.
- (e) If the current dose is the highest dose and the rule indicates dose escalation, we will treat the new patients at the highest dose up to maximum 30 patients.
- (f) If the number of new patients treated at the current dose reaches 15, stop the trial and determine the MTD based on data from enrolled patients.

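### The prose gives 21% and 39% as the DLT-rate limits for changing dose, but these are design inputs; the BOIN boundaries derived from them are 25.3% and 34.4%, and Table 1 escalates at rates where the prose would stay

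*Combined protocol and SAP*

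**What the plan says.** Section 3.1.2 states: "If the probability of DLTs at the current dose level falls below 21%, the dose in the next cohort escalates". It sets de-escalation at a probability above 39% and keeps the dose unchanged in between. The synopsis paragraph on the escalation rule and Section 3.2 give the same two limits. Section 3.1.2 describes the decision as "based on the posterior probability of DLTs from updated information" but gives no prior.

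The prose also sends the reader to the table: "The detailed rule of dose escalation and de-escalation is tabulated in Table 1". Table 1 has columns for 3, 6, 9, 12 and 15 patients. Its row "Escalate if # of DLT" reads 0, 1, 2, 3, 3, and its de-escalation row reads 2, 3, 4, 5, 6.

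The R-code appendix (headed 15.6, cited elsewhere as 15.5) computes 0.3 × 0.7 and 0.3 × 1.3, passes them to the BOIN package as `p.saf` and `p.tox`, and says Table 1 was generated with that package. Section 11.1.2 calls 0.21 to 0.39 an acceptable toxicity range.

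On the denominator, the synopsis bases decisions on "the numbers of patients experiencing DLTs and the total number of patients treated at the current dose level". Section 11.1 enrols in cohorts of 3, and rule (f) under Table 1 says: "If the number of new patients treated at the current dose reaches 15, stop the trial".

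**The concern.** In a BOIN design the two input rates are not the decision limits. They mark DLT rates regarded as clearly too low and clearly too high, and the decision boundaries lie between each of them and the target. The prose gives the inputs the role of the boundaries, so this first-in-human protocol states an escalation limit that its own table does not follow.

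A person working from the prose would reach a different dose from one working from the table in some cells. If a decision fell at a patient count with no column, the printed percentages would be the obvious fallback, and they are not the limits the package derives.

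**Working it through.** **Inputs.** Target 0.30, `p.saf` 0.21 and `p.tox` 0.39 (R-code appendix); Table 1 rows (synopsis); mean sample sizes (Table 2, Section 11.1.2). The documents name the package but do not print the standard BOIN boundary formulas used here.

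**Boundaries.**

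- Escalation: ln(0.79/0.70) / ln[(0.30 × 0.79)/(0.21 × 0.70)] = 0.2532
- De-escalation: ln(0.70/0.61) / ln[(0.39 × 0.70)/(0.30 × 0.61)] = 0.3441

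Escalate if DLTs ≤ n × 0.2532; de-escalate if DLTs ≥ n × 0.3441.

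**Reproducing Table 1, then applying the prose to the observed rate.**

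| n | Table 1 (esc / de-esc) | 0.2532 / 0.3441 | 21% / 39% |
|---|---|---|---|
| 3 | 0 / 2 | 0 / 2 | 0 / 2 |
| 6 | 1 / 3 | 1 / 3 | 1 / 3 |
| 9 | 2 / 4 | 2 / 4 | **1** / 4 |
| 12 | 3 / 5 | 3 / 5 | **2** / 5 |
| 15 | 3 / 6 | 3 / 6 | 3 / 6 |

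The derived boundaries reproduce all ten cells. The prose fails in two: 2/9 = 22.2% and 3/12 = 25.0% both exceed 21%, so it stays where the table escalates. The de-escalation column is the same under 34.4% and 39%.

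**The posterior wording.** With an assumed uniform prior the posterior mean is (x + 1)/(n + 2). At 1/3 it is 2/5 = 0.40, so the prose de-escalates where Table 1 stays. At 1/6 it is 2/8 = 0.25, so the prose stays where Table 1 escalates. This reading does not give Table 1 either.

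**Table 2 mean sample sizes.** Re-simulation used 20,000 trials per scenario, cohorts of three, a start at level 1, a stop at 15 patients on one dose, and an assumed 0.95 elimination cut-off with a uniform prior.

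| Scenario | Printed | 0.253 / 0.344 | 21% / 39% |
|---|---|---|---|
| 1 | 27.7 | 27.9 | 26.6 |
| 2 | 25.1 | 25.2 | 23.4 |
| 3 | 20.1 | 20.2 | 18.8 |
| 4 | 29.2 | 29.0 | 27.7 |
| 5 | 29.8 | 29.8 | 29.4 |
| 6 | 11.3 | 11.4 | 11.1 |

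In scenarios 1 to 5 the 21%/39% values lie 7 to 14 standard errors (for 1000 runs) below print. A hybrid of 0.253 with 0.39 gives exactly the same results as 0.253 with 0.344. Table 2 therefore identifies the escalation limit and says nothing about the de-escalation limit.

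**Sizes outside Table 1, if the titration patient counts.**

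| n | 0.2532 / 0.3441 | 21% / 39% | Differ at |
|---|---|---|---|
| 4 | 1 / 2 | 0 / 2 | 1/4 (25.0%): boundaries escalate, prose stays |
| 7 | 1 / 3 | 1 / 3 | none |
| 10 | 2 / 4 | 2 / 4 | none |
| 13 | 3 / 5 | 2 / 6 | 3/13 (23.1%): boundaries escalate, prose stays; 5/13 (38.5%): boundaries de-escalate, prose stays |

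If titration ends on a DLT and three further patients join that dose, 1/4 arises when all three are free of DLT. That has probability 0.7³ = 34.3% at a true rate of 30%, 0.9³ = 72.9% at 10%, and 0.5³ = 12.5% at 50%.

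**The case against.** The strongest reply is that Table 1 settles every case it covers. Three sections cite it, the appendix gives its script, and the sponsor or its designee assigns each patient's dose (Section 4.4). That stands: no explicit order of precedence is printed, but treating the table as the rule is the fair reading, and within its columns this is an error of wording.

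Second, a reader might infer that Tables 1 and 2 prove a 34.4% de-escalation limit. They do not. At 3, 6, 9, 12 and 15 patients 34.4% and 39% give the same actions, so 34.4% and the 5/13 conflict depend on the formula alone.

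Third, a reader might infer that uncovered decisions are bound to occur. The documents do not support that. The synopsis, Section 3.1.2 and Section 11.1.1 refer to the total or cumulative number treated at a dose, which would include a titration patient. Section 11.1 and rule (f) point to counting cohorts of three only; counts of 4, 7, 10, 13, 16 would step over 15. Figure 1, not available here, may resolve it.

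Fourth, escalating at 1/4 may look like a special hazard. It is no more aggressive than the table itself, which escalates at 3/12, also 25%. Nor is the prose always the more cautious rule: at 5/13 it stays where the boundaries de-escalate.

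**Conclusion.** The concern holds as a misstated threshold. The escalation limit in the prose is wrong against Table 1 in two cells (2/9 and 3/12) and against Table 2's sample sizes. The de-escalation limit is wrong on the BOIN formula, with no evidence either way from the tables. No decision in Table 1's columns is left open, given that the table governs.

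The further exposure is conditional. If only cohorts of three count, it is zero. If the titration patient counts, simulation of scenarios 1 to 5 from level 2 meets at least one of the three off-table conflicts in 23% to 62% of trials when three patients are added to the titration patient, and in 8% to 37% when two are added. Those ranges assume that the rate of grade 2 or higher toxicity is 10, 30 or 50 points above the DLT rate, which the documents do not give.

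A reader might also infer that MTD selection is at risk. Even with the prose applied in every cell, in cohorts of three from level 1, correct selection in scenarios 1 to 5 moves from 58.6, 59.8, 74.4, 55.3 and 54.4% to 59.2, 59.5, 76.3, 51.2 and 54.4% (level 1 taken as the MTD in scenario 3). The effect is mixed, from 4.1 points lower to 1.9 points higher. The point should be fixed, but it does not undermine the design.

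**What to change.** In the synopsis and Sections 3.1.2 and 3.2, describe 0.21 and 0.39 as design inputs. State that the dose escalates at an observed DLT rate of 0.253 or less and de-escalates at 0.344 or more, and that Table 1 governs. Replace the posterior-probability wording with the observed rate.

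State whether the titration patient counts in the denominator, and whether the expanded cohort adds three patients or two. If the patient counts, add columns for n = 4, 7, 10 and 13: escalate at ≤ 1, 1, 2, 3 and de-escalate at ≥ 2, 3, 4, 5. Eliminate entries for these columns need a stated elimination cut-off. The printed eliminate entry of 6 at n = 9 (5 at a 0.95 cut-off) is a separate point and should be raised on its own.

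The cost is wording in three places, a short statement on counting, and at most four columns. Aligning the prose with Table 1 changes no rule. Adopting 21% and 39% as the actual limits would change the escalation rule, which Section 13.1 lists among amendments needing ethics approval, and Tables 1 to 3 would have to be rerun.

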### **3.2. Justification of dose levels and starting dose**

Six dose levels are planned: 250, 500, 750, 900, 1200, 1500 mg flat dose. The reason for using flat dosing instead of body weight-adjusted dosing is based on previous population pharmacokinetic studies for multiple monoclonal antibody drugs[3, 16, 17]. Patients will be assigned to a dose level in the order of study entry. The starting dose of 500 mg (dose level 2)

is based on ICH guidance and determined to be equal to 1/6 of the human equivalent dose of the highest non-severely toxic dose (HNSTD)[4, 18].

In BOPIN design, the decision to escalate or de-escalate is based on the probability of toxicities from updated information on pre-defined toxicity rate, which is set at 30% in this study. When the probability of DLT is lower than 21% (70% of target rate), the dose in the next cohort escalates to the next level. By contrast, when the probability of DLT is higher than 39% (130% of target rate), the dose in the next cohort de-escalates to the next lower level. The enrollment continues until the maximum of 30 patients is reached.

The rule of dose escalation and de-escalation is tabulated in Table 1.

There are two early stopping rules set in this study.

- Stop the trial if the lowest dose (dose level 1, i.e. 250 mg) is eliminated due to overt toxicities.
- Stop the trial and estimate the MTD if the number of new patients treated at the current dose level reaches 15

The detailed statistical methods for dose escalation and de-escalation and determination of MTD are described in Section 11. Description of Statistical Methods. The detailed R script for this study is described in Section 15.5.

### **3.3. Treatment duration**

If the patients experience no adverse reactions that lead to treatment delay or discontinuation, treatment continues weekly until disease progression, to the maximum of one year, withdrawal from study or death, whichever comes first.

Detailed procedures for the evaluation and treatment are described in Section 7.2.

Toxicities will be evaluated and graded by the NCI Common Terminology Criteria for Adverse Events (CTCAE) 4.0 or until the toxicities revert to grade  $\leq 1$ .

Serial serum samples will be collected during the 1st and 4th week of 1st cycle of treatment at scheduled time points for determination of the PK of HLX06. Additional time points include before and after 2nd and 3rd infusions in cycle 1. Thereafter, the blood levels of HLX06 will be measured before and after the first infusion in each cycle up to 24 weeks, , and on the 28-day follow-up visit (Follow-up Visit 1) whenever possible.

This study also incorporates optional pharmacodynamic study by examining the serum levels of VEGF-A, soluble VEGFR-1, soluble VEGFR-2 before and after first and 4th infusion in cycle 1 in conjunction with pharmacokinetic studies.

### **3.4. Follow-up period**

The details of follow-up are described in Section 7.3.

### **3.5. Primary endpoints of the study**

- Primary outcome measures
- Numbers and percentage of patients with adverse events (AEs).
- Maximum tolerated dose of HLX06.

### **3.6. Secondary endpoints of the study**

- Maximum concentration ( $C_{\max}$ ) in different cohorts.
- Minimum concentration ( $C_{\min}$ ) in different cohorts.
- Area under concentration ( $AUC_{0-\tau}$ ) in different cohorts.
- Half-life ( $T_{1/2}$ ) of HLX06 in different cohorts.
- Clearance (CL) rate of HLX06 in different cohorts.
- Volume of distribution ( $V_{ss}$ ) at steady state in different cohorts.
- The presence and percentage of anti-HLX06 antibody (immunogenicity).
- Disease control rate
- Overall response rate.
- Duration of response

## **4. STUDY ENROLLMENT AND WITHDRAWAL**

### **4.1. Study population**

A maximum of 30 patients will be enrolled (if no patients require replacement). Patients with metastatic or recurrent solid tumors who have failed standard therapy can be considered eligible for enrollment.

### **4.2. Inclusion criteria**

- Eligible patients must be 18-years of age or older or per local regulations.
- Patients with histologically-proven measurable or evaluable advanced or metastatic solid tumors who have failed standard therapy or for whom no standard therapy is available. (For patients with hepatocellular carcinoma, the diagnosis needs to be supported by dynamic CT/MRI, if pathological confirmation is not attainable)
- Eastern Cooperative Oncology Group (ECOG) performance status of  $\leq 2$  at the time of study entry.
- Able to provide informed consent.
- A life expectancy longer than three months.
- Adequate hematologic functions, as defined by: absolute neutrophil counts  $\geq 1500/\text{mm}^3$ ; a hemoglobin level  $\geq 10 \text{ gm/dL}$ ; a platelet count  $\geq 100,000/\text{mm}^3$ .
- Adequate hepatic function defined by: a total bilirubin level  $\leq 1.5x$  of upper limit of normal (ULN); aspartate transaminase (AST) and alanine transaminase (ALT) levels  $\leq 2.5 \times$  of ULN or  $\leq 5x$  of ULN in known hepatic metastases or with primary hepatocellular carcinoma.
- Adequate renal function, as defined by the creatinine clearance rate  $\geq 50 \text{ mL/minute}$  by Cockcroft-Gault formula.
- Adequate cardiac function defined as left ventricular ejection fraction (LVEF) $\geq 50\%$ .
- Use of effective contraceptive measures if procreative potential exists.
- At least 28 days from prior major surgery, prior cytotoxic chemotherapy, or prior therapy with investigational agents (or medical device) or local radiotherapy before 1st infusion of HLX06.
- For patients with hepatocellular carcinoma, their Child-Pugh score has to be A.
- Able to be followed up as required by the study protocol.
-

The ECOG performance table is listed in Appendix 15. Detailed the Child-Pugh score is listed in Appendix 15.2.

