## 1. BACKGROUND INFORMATION AND SCIENTIFIC RATIONALE

### 1.1. Background Information

Angiogenesis plays an important role in cancer development. More than a dozen different proteins have been identified as angiogenic activators, including vascular endothelial growth factor (VEGF), basic fibroblast growth factor, angigenin. The VEGF family and their receptors (VEGFR) are well characterized for their role in neoplastic angiogenesis. The best known monoclonal antibody targeting angiogenesis is bevacizumab (Avastin®). Bevacizumab has been approved for multiple cancers, including lung, ovarian, colorectal and brain cancer (<https://www.avastin.com>). Among them, VEGFR2 belongs to type V receptor tyrosine kinase encoded by KDR gene, and is expressed in vascular endothelial cells. It is a primary responder to vascular endothelial growth factor signal that regulates endothelial migration and proliferation. The expression of VEGFR2 can be found in multiple tumor types, including angiosarcoma, Kaposi sarcoma. In epithelial carcinoma, VEGFR2 expression can be found in mesothelioma, non-small cell lung cancer, and embryonal carcinoma[7]. The tissue levels of VEGF-C and VEGFR2 significantly correlate with the progression and prognosis of cancer.[8]

Targeting angiogenesis using either small molecule inhibitors or biological agents have been widely used in current cancer management. Current approved anti-angiogenesis biological agents include bevacizumab, ramucirumab, afibbercept. Among them, ramucirumab (IMC-1121B) targets vascular endothelial growth factor receptor 2 (VEGFR2). Ramucirumab has been approved for use in combination with paclitaxel for second-line treatment of patients with advanced gastric or gastroesophageal junction adenocarcinoma[9].

Ramucirumab is a fully human IgG1 monoclonal antibody that binds with high affinity to the extracellular domain of VEGFR2. It was discovered from an antibody phase display library from pooled B lymphocytes of healthy human donors. The EC50 of ramucirumab is approximately 0.15 nM. A crystal structure analysis demonstrates the binding of its Fab to domain 3 of VEGFR2 near N-terminus. It blocks the VEGF signaling by both steric blocking of its ligand and changing the receptor conformation[9].

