#### **4.3. Exclusion criteria**

- Patients with large centrally located pulmonary lesions adjacent to or invading large blood vessels.
- Hemoptysis more than  $\frac{1}{2}$  teaspoon (approximately 2-3 mL) of red blood per day.
- Patients who still have  $\geq$  grade 2 toxicities from prior therapies.
- Concurrent unstable or uncontrolled medical conditions with either of the followings:
  - Active systemic infections;
  - Poorly controlled hypertension (systolic blood pressure  $\geq$  160 mmHg or diastolic blood pressure  $\geq$ 100 mmHg), or poor compliance with anti-hypertensive agents;
  - Clinically significant arrhythmia, unstable angina pectoris, congestive heart failure (class III or IV of New York Heart Association [NYHA]) or acute myocardial infarction within 6 months;
  - Uncontrolled diabetes or poor compliance with hypoglycemics;
  - The presence of chronically unhealed wound or ulcers
  - Other chronic diseases, which, in the opinion of the investigator, could compromise safety of the patient or the integrity of study.
- Newly-diagnosed or symptomatic brain metastases (patients with a history of brain metastases must have received definitive surgery or radiotherapy, be clinically stable, and not taking steroids for brain edema). Anticonvulsants are allowed.
- Any concurrent malignancy other than basal cell carcinoma or carcinoma in situ of the cervix. (Patients with a previous malignancy but without evidence of disease for  $\geq$  3 years are allowed to participate).
- Pregnancy (confirmed by serum beta human chorionic gonadotropin [ $\beta$ HCG]) or breast-feeding (for female patients only).
- A known history or clinical evidence of a deep vein or arterial thrombosis, or pulmonary embolism within 6 months of first infusion of HLX06.
- Less than six weeks from last infusion of ramucirumab, or any other anti-VEGF monoclonal antibody therapy (Last treatment with other monoclonal antibodies targeting proteins other than anti-angiogenic factors is permitted if  $\geq$  4 weeks prior to the first infusion of HLX06).

- Proteinuria  $\geq 2+$  in routine urinalysis (patients with a protein value of  $\leq 500$  mg confirmed by a 24-hour urine collection are eligible).
- Known history of human immunodeficiency virus infection (HIV).
- The patient is the investigator, sub-investigator or any one directly involved in the conduct of the study.

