## **6. ASSESSMENT OF SAFETY AND MANAGEMENT OF TOXICITIES**

### **6.1. Dose limiting toxicities (DLTs)**

DLTs are side effects of a drug or other treatment that are serious enough to prevent an increase in dose or level of that treatment in a clinical study. We use Common Toxicity Criteria for Adverse Events (CTCAE) 4.0 for grading of toxicities in this study.

The definition of DLTs in this study is the toxicities during the first cycle of treatment:

A DLT will be considered to be IP-related unless there is a clear, well-documented, alternative explanation for the toxicity. Delayed DLTs are adverse events that meet the criteria of DLTs that occur after the first cycle of treatment. Delayed DLTs need to be evaluated on a case-by-case basis to make sure that there is no cumulative damage to vital organ function.

Delayed DLTs will also be considered to estimate the MTD for HLX06 in this study.

All adverse events that meet DLT or delayed DLT criteria, as well as any Grade 3 or 4 infusion reactions no matter whether the event is a DLT must be reported to the Sponsor or its designee, within 24 hours.

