### **6.4. Management of possible toxicities**

HLX06 has not been used in human beings before. There is no clinical experience to define expected toxicities to humans. Based on its mode of action, the spectrum of toxicities is expected to be similar to what have been described for anti-angiogenesis agents, such as bevacizumab, ramucirumab or other small molecule inhibitors for anti-angiogenesis (e.g. sunitinib, sorafenib). The following are the common or severe toxicities by bevacizumab and ramucirumab and their respective management.

**Allergic reaction/hypersensitivity and infusion-related reactions:** Fever, chills, shakes, itching, rash, hyper- or hypotension, difficulty breathing. It is likely that most infusion-related adverse events will occur within the first 24 hours after beginning the infusion, and may be treated by slowing or interruption of the infusion, or with supportive treatment as indicated. The common agents used to treat hypersensitivity agents are anti-histamine, H2-blockers, corticosteroid. Severe anaphylactic reactions might require epinephrine treatment. Infusion reaction should be graded according to NCI CTCAE criteria. Treatment recommendations are as follows:

- **Grade 1 symptoms:** If the Investigator assesses that it is a mild reaction and infusion interruption is not indicated, the prophylactic pre-medications are recommended: diphenhydramine 30-50 mg (depending on institutional availability or equivalent medications), acetaminophen 325-500 mg PO at least 30 minutes before additional IP infusion.
- **Grade 2 symptoms:** If the Investigator assesses that it is a moderate reaction, requiring therapy or infusion interruption, stop the IP infusion and begin with intravenous infusion of normal saline, and treat the patients with diphenhydramine 30-50 mg (or equivalent medications) intravenously, and dexamethasone 10 mg (or corticosteroids with equivalent potency) intravenously. After the symptoms have subsided, restart the infusion at 50% of original infusion rate. Monitor the patient closely. If the symptoms recur, no further IP infusion at that visit. Prophylactic pre-medications with diphenhydramine, acetaminophen and corticosteroid are indicated for future infusion of IP.

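### The washout criteria set no minimum interval for approved small-molecule anti-angiogenic inhibitors, so carry-over can reach the DLT count and the pharmacodynamic baseline

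*Combined protocol and SAP*

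**What the plan says.** The washout rules appear in the synopsis and again, in the same terms, in sections 4.2 and 4.3.

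- **28 days (4.2):** "At least 28 days from prior major surgery, prior cytotoxic chemotherapy, or prior therapy with investigational agents (or medical device) or local radiotherapy".
- **Six weeks (4.3, exclusion):** "Less than six weeks from last infusion of ramucirumab, or any other anti-VEGF monoclonal antibody therapy".
- **Four weeks (4.3):** "Last treatment with other monoclonal antibodies targeting proteins other than anti-angiogenic factors is permitted if" at least 4 weeks have passed before the first HLX06 infusion.

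Elsewhere the protocol shows that it has other anti-angiogenic drugs in view. Section 6.4 expects the toxicities of HLX06 to resemble those of anti-angiogenic agents, among them "other small molecule inhibitors for anti-angiogenesis (e.g. sunitinib, sorafenib". Section 1.1 states: "Current approved anti-angiogenesis biological agents include bevacizumab, ramucirumab, afibbercept".

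On attribution, section 6.1 states: "A DLT will be considered to be IP-related unless there is a clear, well-documented, alternative explanation for the toxicity". On pharmacodynamics, section 9.2 samples VEGF-A and soluble VEGFR-1 and VEGFR-2 before and after each cycle 1 infusion, and section 11.3.8 compares both raw values and values relative to baseline.

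**The concern.** Washout is defined by drug class, and one class that the protocol itself links to HLX06 toxicity is missing. An approved small-molecule anti-angiogenic inhibitor is not cytotoxic chemotherapy, not an investigational agent and not a monoclonal antibody.

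The trial enrols patients whose standard therapy has failed or for whom none exists. It expressly admits liver cancer: "For patients with hepatocellular carcinoma, their Child-Pugh score has to be A". Some patients may therefore arrive from such a drug.

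Two results are exposed. The first is the primary endpoint: a toxicity of the earlier drug that appears in the first four weeks counts against HLX06 unless another cause is clearly documented. The second is the pharmacodynamic comparison: a pre-dose sample taken under residual inhibition of the same pathway is not an untreated baseline.

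**Working it through.** **Step 1. Is the class covered anywhere?** The places that could set an interval are the eligibility lists, the screening rules and the rules on concomitant treatment.

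| Place | What it controls | Minimum interval for an approved small-molecule inhibitor? |
|---|---|---|
| Synopsis, 4.2 | Surgery, cytotoxic chemotherapy, investigational agents or devices, local radiotherapy: 28 days | No, class not named |
| Synopsis, 4.3 | Anti-VEGF antibodies: six weeks; other antibodies: 4 weeks | No, antibodies only |
| 4.3 | Residual toxicity of grade 2 or higher; pressure of 160 systolic or 100 diastolic and above; proteinuria | No, acts on visible toxicity |
| 7.1 | Screening completed within 28 days before infusion 1 | No, a maximum only |
| 7.5 | Medications in the 28 days before infusion 1 are recorded | No, recording only |
| 7.5.1 | Other anti-neoplastic treatment barred during the study | No, see step 2 |

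**Step 2. Does section 7.5.1 close the gap?** Section 7 divides each patient's study into screening, treatment and follow-up. Read with that, the ban in 7.5.1 can be taken to start at consent, so the earlier drug would have to stop then. The time from consent to infusion 1 has no stated minimum, so the drug-free interval has none either.

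**Step 3. What can one misattributed event do?** In the acceleration phase (synopsis, 3.1.1), one first-cycle DLT ends single-patient cohorts. So does the second first-cycle toxicity of grade 2 or higher, and that trigger states no attribution test.

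For the later cohorts, first reproduce Table 1. The inputs are the target 0.30, safety bound 0.21 and toxicity bound 0.39 (sections 3.1.2 and 15.6).

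- Escalation limit: ln(0.79/0.70) / ln[(0.30 × 0.79)/(0.21 × 0.70)] = 0.2532
- De-escalation limit: ln(0.70/0.61) / ln[(0.39 × 0.70)/(0.30 × 0.61)] = 0.3441

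Multiplying by n = 3, 6, 9, 12, 15, and rounding down and up respectively, gives escalate at 0, 1, 2, 3, 3 and de-escalate at 2, 3, 4, 5, 6. Both rows match Table 1. With three patients, 0 to 1 DLT turns escalate into stay, and 1 to 2 turns stay into de-escalate.

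**Step 4. How sensitive are the decisions?** This is an illustration, because the documents give no carry-over rate. Let p be the true HLX06 DLT rate and c the average carry-over DLT risk per patient, which is the share exposed times the risk in an exposed patient. The observed rate is q = 1 − (1 − p)(1 − c). The chance of escalating after three patients is (1 − q)³. The chance of de-escalating is the binomial probability of two or more DLTs in three. Take p = 0.10:

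| c (assumed) | q | P(no DLT in a single-patient cohort) | P(escalate, n = 3) | P(2 or more DLTs, n = 3) |
|---|---|---|---|---|
| 0 | 0.100 | 0.900 | 0.729 | 0.028 |
| 0.05 | 0.145 | 0.855 | 0.625 | 0.057 |
| 0.10 | 0.190 | 0.810 | 0.531 | 0.095 |
| 0.20 | 0.280 | 0.720 | 0.373 | 0.191 |

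**Step 5. The pharmacodynamic baseline.** None of the controls in step 1 acts on it, because they respond to visible toxicity or only record exposure. In a one-patient cohort, an affected patient supplies that cohort's whole baseline.

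**The case against.** The case against is substantial, and parts of it stand.

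- **Other controls exist.** Patients with residual toxicity of grade 2 or higher, poorly controlled hypertension or marked proteinuria are excluded. Prior tumour therapy is recorded at screening (7.1.1), eligibility questions go to the Medical Monitor (7.1), and the sponsor assigns each dose level (4.4). The records could support the alternative explanation that 6.1 allows. The DLT thresholds are also high. All this lowers the risk to the DLT count. It does not remove it: when two drugs share a toxicity profile, a clear alternative explanation is hard to document, and residual drug without visible toxicity passes every criterion.
- **The error is in the cautious direction.** Misattribution slows escalation. That is true, but it can also lower the selected MTD and use up part of a maximum of 30 patients.
- **Pharmacodynamics is minor.** Section 11.2.5 calls it exploratory, and section 3.6 lists no such endpoint. It is nonetheless a secondary objective (2.2).

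A reader might infer several stronger things that the documents do not support.

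- That a patient may take the earlier drug up to the day before infusion 1. Sections 7 and 7.5.1 together arguably forbid it from consent. What is missing is a guaranteed interval.
- That the third biological agent in section 1.1 certainly escapes the six-week rule. That needs the fact that it is not a monoclonal antibody, which the documents do not state.
- That the antibody intervals prove an intention to prevent carry-over. Only the six-week interval exceeds 28 days, and section 6.4 mentions the long half-life of antibodies, which could equally explain it.
- That sorafenib is the expected prior drug in liver cancer. The documents do not say so.

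**Conclusion.** The gap is certain: the synopsis and sections 4.2 and 4.3 set no minimum interval for a drug class that section 6.4 places alongside HLX06 for toxicity. Carry-over can therefore affect the end of acceleration, the Table 1 decisions that feed the MTD, and the relative-to-baseline pharmacodynamic results.

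Its size is unknown. One event is enough to change a decision, but the documents do not give the number of patients affected, how long these drugs persist, or how far they shift the markers. The probabilities shown rest on an assumed p of 0.10, assumed values of c from 0 to 0.20, and independence between the two sources of DLT. A reader should not conclude that the DLT count will be biased, only that the eligibility text permits it.

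**What to change.** - In the synopsis and section 4, add approved small-molecule anti-angiogenic (VEGFR-targeted) agents to the washout criterion, so that it agrees with section 6.4. The sponsor should set and state the interval; none is proposed here.
- In section 4.3, state whether the six-week rule for anti-VEGF antibodies also covers the other anti-angiogenic biological agent listed in section 1.1. This matters only if that agent is not a monoclonal antibody, which is an assumption here.
- In section 7.5.1, say whether the ban on other anti-neoplastic treatment starts at consent.

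The criterion need not be widened to all systemic anticancer therapy. That would bring in hormonal treatment, and the protocol anticipates patients with prostate cancer.

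The cost is a short amendment to the eligibility wording. Some patients coming off an oral inhibitor would start HLX06 later; the documents do not say how many.
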